## 1. Thai title

การศึกษานำร่องการทดสอบภูมิคุ้มกันต่อเชื้อไวรัสเดงกีหลังได้รับวัคซีนไข้เลือดออกเชื้อเป็นอ่อนฤทธิ์ชนิดสี่สายพันธุ์เข้าผิวหนัง  
ในกลุ่มอาสาสมัครสุขภาพดี

## 2. English title

Immunogenicity of an intradermal live attenuated tetravalent dengue vaccine among healthy volunteers:  
A pilot study

## 3. Keywords

**English:**...Dengue, Intradermal vaccination, Immunogenicity, T cell response, Tetravalent dengue  
vaccine

## 5. Details of proposal

### 5.1 Background

Dengue fever, caused by the dengue virus (DENV), represents a significant global health challenge, particularly in tropical and subtropical regions. This disease affects millions of individuals annually, resulting in severe morbidity and a substantial economic burden. Advanced age is a significant risk factor for increased severity and mortality associated with this condition, predicting an escalating impact in the future. In the absence of specific antiviral treatments, the development and implementation of effective vaccination strategies are crucial in mitigating the impact of dengue fever.

Qdenga, a live attenuated tetravalent dengue vaccine traditionally administered subcutaneously, has shown promising results in conferring immunity against all four dengue serotypes, this one also not need to check for previous infection as concerning of enhancing antibody as the previous Dengvaxia vaccine, promoting more opportunity.

## 5.2 Study setting background

Intradermal vaccination is an established method known to enhance immunogenicity by targeting the rich network of antigen presenting cells present in the dermis, WHO have done a literature review in 2009 for studies about intradermal injection proposed that a fractional ID dose can induced adequate immune responses in healthy persons for variable type of vaccines, including those for rabies, yellow fever, poliomyelitis, seasonal influenza and there also be more others recent studies focusing on the COVID-19 vaccination as vaccine inequity remains a challenge across the globe.

## 5.3 Rationale

As in the setting of low- to middle-income countries, to demonstrating that lower doses of vaccine via intradermal route can still elicit robust immune responses, thereby lowering the overall cost of vaccination might be particularly meaningful ,with possible extra benefit of experiencing fewer side effects or risk of allergy. This study goal is to explores the potential of intradermal administration of Qdenga, hypothesizing that a lower dose via this route could achieve adequate immunogenicity compared to the standard subcutaneous administration, thus offering a cost-effective alternative particularly in low-resource settings where dengue is most prevalent.

## 5.4 Objectives

### Primary Objectives

1. To evaluate the antibody response to dengue virus following administration of the second dose of QdengaTM via the intradermal route.
2. To evaluate the T-cell response (CD4 and CD8) to dengue virus following administration of the second dose of QdengaTM via the intradermal route.

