### 5.7.8 Study variables and their definition

Independent variables

- Technique of vaccination: subcutaneous vs. intradermal
- Sex
- Age

Dependent variables

- ELISA: Antibody level for dengue at day 0, 30, 120
- ELISpot: T cell responses against dengue antigens at day 0, 30, 120
- Adverse event following vaccine (AEFI)

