##### Antibody analysis

- Detection of dengue-specific human Abs by ELISA
- Mixtures of all four DENV serotypes were captured onto a MAXISORP immunoplate (NUNC) coated with mouse anti-E antibody (4G2) or anti-NS1 antibody (NS1-F3). DENV captured wells were then incubated with B cell line (BCL) culture supernatants followed

by alkaline phosphatase (AP)-conjugated anti-human IgG Abs. The reaction was visualized by the addition of PNPP substrate. The reaction was stopped with NaOH.

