### **T cell responses**

#### ELISpot assay

Briefly, PBMCs were added to polyvinylidene difluoride-backed plates (Millipore) precoated with a monoclonal antibody to IFN- $\gamma$  (1-DIK; MABTECH). Peptides were then added at a final concentration of 10  $\mu$ M and the PBMCs were cultured overnight. Cells were discarded and spots were revealed by incubation with biotinylated monoclonal antibody to IFN- $\gamma$  (MABTECH) followed by streptavidin-conjugated alkaline phosphatase and substrate. The spots were counted using an AID-ELISpot Reader (Autoimmun Diagnostika). The number of specific T-cell responders was calculated after subtracting negative control values.

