#### **Peptides**

[figure not shown]
- 15-mer peptides overlapping by 5 amino acids corresponding to sequences of dengue serotype 2 strain 16681 (CprM, E, NS1, NS2, NS3, NS4, and NS5) and to the NS3 sequences of dengue serotype 1 strain Hawaii, dengue serotype 3 strain H87, and dengue serotype 4 strain H241 were synthesized to >80% purity (Sigma Aldrich). Lyophilized peptides were resuspended in dimethyl sulfoxide (DMSO; Sigma) at 80 mg/mL for peptide mixtures. The overlapping peptides were grouped together in pools corresponding to individual dengue proteins (dengue 2: CprM-26, E-97, NS1-71, NS2-70, NS3-123, NS4-70, NS5-95, dengue 1 NS3-124, dengue 3 NS3-124, and dengue 4 NS3-124). The final concentration of any single peptide was 2  $\mu$ g/mL, and the final concentration of DMSO was <1% in all experiments.

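### Primary objective 2 names CD4 and CD8, but the only T-cell assay described cannot separate them; the ELISA text names a specimen the study does not produce and leaves the capture antibody open

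*Combined protocol and SAP*

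**What the plan says.** Section 5.4 of the combined protocol and SAP sets two primary objectives, one for antibody and one for T cells. The second reads "To evaluate the T-cell response (CD4 and CD8) to dengue virus following administration of the second dose". Section 5.7.8 lists one outcome variable for each: "ELISA: Antibody level for dengue at day 0, 30, 120" and "ELISpot: T cell responses against dengue antigens at day 0, 30, 120".

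Section 5.7.9 describes the assays.

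- **T cells.** Under ELISpot assay, "PBMCs were added to polyvinylidene difluoride-backed plates (Millipore) precoated with a monoclonal antibody" to IFN-gamma. The result is given as follows: "The number of specific T-cell responders was calculated after subtracting negative control values". Under Peptides, "The overlapping peptides were grouped together in pools corresponding to individual dengue proteins".
- **Antibody.** Under Antibody analysis, virus of all four serotypes is captured on plates coated with an anti-E antibody or an anti-NS1 antibody. Then "DENV captured wells were then incubated with B cell line (BCL) culture supernatants", and binding is detected with an anti-human IgG conjugate.
- **Specimens.** Under Blood collection and Sample preparation, participants give clotted and heparinised blood, and serum, plasma and PBMCs are stored.

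**The concern.** Each primary objective depends on one assay, and in each case the assay text does not deliver what the objective and the variable list call for.

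For T cells, the objective names two subsets and the assay reports neither. A report that followed the objective's wording would invite a statement about CD4 or CD8 responses that these data could not support.

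For antibody, the text taken literally measures something other than the participants' antibody. Even with the specimen corrected, two capture antibodies stand behind one variable. Unless one is named beforehand as primary, the choice could be made after the results are seen.

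**Working it through.** The plan gives no figure to reproduce on this point, and no power, variance or error-rate input bears on it. The check sets the passages side by side.

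**T-cell objective against T-cell assay**

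1. Named in the objective (5.4): CD4 and CD8, so 2 subsets. Neither is named anywhere else in the readable text.
2. Outcome variable (5.7.8): one ELISpot variable, with no subset.
3. Cells plated (ELISpot assay): PBMCs. No depletion, sorting or staining step is described.
4. Stimulus (Peptides): pools defined by dengue protein. None is assigned to CD4 or CD8.
5. Result (ELISpot assay): background-subtracted responders, not split by subset.

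A spot shows that a cell secreted IFN-gamma, but not which subset the cell belongs to. That has to come from the cells plated, from the stimulus or from a second readout, and none of these is specified by subset. Subset-specific results described: 0 of 2.

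**Antibody variable against ELISA text**

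1. Variable (5.7.8): a dengue antibody level by study day, which can only be the participant's own.
2. Participant specimens stored that could supply it (Sample preparation): serum and plasma, so 2.
3. Participant specimens named in the ELISA step (Antibody analysis): 0. The only material named is B-cell-line supernatant.
4. Source of B-cell lines: none. No section derives them from participants or obtains them elsewhere.

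**Capture antibody against the variable**

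1. Captures named: 2 (anti-E, anti-NS1), joined by *or*.
2. Antibody variables: 1.
3. Rule for which capture is used, or which is primary if both are: none stated.

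The two captures hold different viral proteins on the plate, so their readings need not agree. With either one, all four serotypes share a well and the conjugate detects IgG. The assay therefore measures total dengue-binding IgG, not a serotype-specific response. This does not conflict with objective 1, which asks only for the antibody response to dengue virus, but it limits what can be concluded.

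**The case against.** The strongest reply is that these are drafting faults in a 24-participant pilot.

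On T cells, the parenthesis can be read as a response that includes both subsets. A total IFN-gamma ELISpot would then fit the objective. The ELISpot paragraph also presents itself as a brief summary, so a step may have been left out. The plan promises no CD4-versus-CD8 comparison, and PBMCs are frozen for later work. All of this stands, and it lowers the severity. It does not remove the point: on the inclusive reading the objective should say so, and an omitted step that determines a primary result should be written down.

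On antibody, the paragraph's own title refers to human antibodies, the variable list is by participant visit, and serum and plasma are kept. Staff would very likely test those. This also stands. The specimen still has to be named correctly, and the open choice of capture remains after that correction.

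A reader might go further and infer three things that the documents do not support:

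- **That the study cannot fill the gap stated in section 5.5.** That section speaks of humoral and cell-mediated immunity without naming subsets, and a total ELISpot is a cell-mediated measure.
- **That the statistical section confirms the lack of a subset endpoint.** It names no outcome at all, so its silence on subsets shows nothing.
- **That the peptide panel is unsuitable, because for serotypes 1, 3 and 4 it covers NS3 only.** The objective concerns the response to dengue virus, and the inclusion criteria require dengue IgG at entry. The choice of pools contradicts no objective.

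**Conclusion.** The point holds as a mismatch between the primary objectives and the assay text. It should be fixed, but it does not invalidate the design. Its size is 0 of 2 named subsets resolved, 0 of 2 stored participant specimens named in the ELISA step, and 2 capture antibodies for 1 antibody variable.

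A reader might infer that participants' antibody will not be measured, or that samples are lacking. The documents do not support that: serum and plasma are collected and stored, no B-cell line exists to be tested, and carried-over text is the likelier explanation.

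The finding covers the readable text only. One figure under Peptides was not available to this review. It also assumes that no separate laboratory document adds a subset-resolving step or corrects the specimen.

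**What to change.** 1. **Objective 2 (5.4).** Restate it as the total, not subset-resolved, IFN-gamma T-cell response to dengue antigens, and limit the conclusion to that. If CD4 and CD8 results are intended, describe in 5.7.9 the method that resolves them and add the matching variables to 5.7.8.
2. **Antibody analysis (5.7.9), specimen.** Replace the B-cell-line supernatants with participant serum or plasma.
3. **Antibody analysis (5.7.9) and 5.7.8, capture.** Prespecify whether anti-E or anti-NS1 capture gives the primary antibody level, and limit the antibody conclusion to total dengue-binding IgG.

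With objective 2 restated, the cost is wording only: no new samples, wells or visits. If the sponsor keeps subset results, the cost depends on the method chosen and cannot be estimated from the documents.

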### Secondary Objective

1. To assess the safety and reactogenicity of intradermal administration of Qdenga.

## 5.5 Literature review

Dengue fever, attributable to the dengue virus, represents a substantial global health concern. The advent of vaccines such as Qdenga and Dengvaxia has demonstrated potential in conferring immunity

against all four serotypes of the dengue virus. However, given the higher prevalence of dengue fever in resource-limited tropical regions, it is crucial to explore cost-reduction strategies. Intradermal injection, a previously successful dose-sparing technique, offers one such strategy. Nonetheless, the efficacy of intradermal administration for the newly developed Qdenga vaccine remains uncertain and warrants further investigation.

Study on the immunogenicity of the Qdenga vaccine, given subcutaneously, have shown promising results. One randomized, placebo-controlled Phase 2 study involving 148 participants aged 1.5 to 45 revealed seropositivity rates at month 36 of 97.3%, 98.7%, 88.0%, and 56.0% for DENV-1, -2, -3, and -4, respectively. Notably, seropositivity for DENV-4 varied significantly based on initial serostatus, with 89.5% in seropositive individuals compared to 21.6% in seronegative individuals. No vaccine-related serious adverse events (SAEs) were reported. The study demonstrated the persistence of neutralizing antibody titers and the Qdenga vaccine's tolerability over three years in both children and adults living in dengue-endemic regions.

A key concern with the dengue vaccine is the potential side effects, including transient vaccine viremia. After receiving the Qdenga vaccine, 49% of previously uninfected participants and 16% of those previously infected with dengue experienced vaccine viremia. This viremia typically began in the second week post-vaccination, lasted an average of four days, and was associated with mild to moderate symptoms such as headache, joint pain, muscle pain, and rash in some subjects. During this period, dengue diagnostic tests may yield positive results, making it difficult to distinguish between vaccine viremia and wild-type dengue infection. A study on IgG, IgM, and nonstructural protein 1 (NS1) response profiles post-Qdenga vaccination indicated that IgM and IgG profiles within 30 days of vaccination were similar to those observed during natural dengue infections, though no NS1 antigen was detected. As previously proposed that lower dose of vaccine might be associated with possible extra benefit of experiencing fewer side effects or risk of allergy, intradermal reduced dosed sound compelling.

Qdenga vaccine was also called TAK-003/DENVax in previous study, it was based on a live-attenuated DENV-2 strain (PDK-53-V) in which the premembrane (prM) and envelope (E) genes have been replaced by the homologous genes from each one of the four DENV serotypes. The recommendation for using the subcutaneous route in dengue vaccine administration is based on findings from certain Phase I studies. One such study assessed the safety and immunogenicity of a recombinant live attenuated tetravalent dengue vaccine (DENVax) in 96 flavivirus-naive healthy adults in Colombia. Participants in this study were randomized to receive either a high-dose formulation of DENVax or a placebo via

subcutaneous or intradermal injection. The study results indicated that both intradermal and subcutaneous routes elicited tetravalent dengue immune responses. However, the subcutaneous route was associated with a lower incidence of local adverse events compared to the intradermal route, although the difference was not statistically significant..

Another study evaluated the safety and immunogenicity of an early low-dose tetravalent dengue vaccine candidate (LD-TDV), which uses an attenuated serotype 2 backbone, administered intradermally either with an injector device (PharmaJet) or a needle-syringe in 67 subjects. The findings indicated that the intradermal administration of LD-TDV was well tolerated, with no significant safety concerns, and induced an immune response against all four dengue serotypes. The overall tetravalent seroconversion rates were 13.8% at Day 28 and 31.0% at Day 118, comparable to the previously reported 25% seroconversion rate for low-dose TDV given intradermally in 72 flavivirus-naive adults. Local reactions, such as induration (91.7% vs. 12.5%;  $P < .0001$ ) and pruritus (50% vs. 8.3%;  $P = .0034$ ), were more frequent following intradermal vaccination compared to subcutaneous administration. Most of these reactions were mild and resolved within one day.

This study aims to ensure the safety of vaccine recipients by comparing the administration of a second dose via the intradermal (ID) route after an initial subcutaneous (SC) dose with a control group receiving both doses subcutaneously (SC-SC). Previous research in Thailand on COVID-19 vaccines also evaluated the safety and immunogenicity of fractional (1/5th or 1/6th) doses of homologous ChAdOx1 or BNT162b2 administered intradermally following an initial intramuscular (IM) dose, demonstrating safety and immunogenicity. Based on this, the study hypothesizes that intradermal administration of fractional doses of the Qdenga vaccine after an initial SC dose will be immunogenic and have acceptable systemic adverse effects, with potential utility as a booster in the future.

The potential of intradermal vaccination to maintain or enhance immunogenicity while reducing the required dose has been highlighted in several reviews. This method could lower costs and improve vaccine accessibility in low-resource settings. However, further research is needed, as no randomized studies have yet evaluated both humoral and cell-mediated immune responses to intradermal Qdenga vaccination.

[figure not shown]
## 5.6 Conceptual framework

A new dengue vaccine, Qdenga™, has recently become available in Thailand. As a live-attenuated vaccine, it does not require pre-vaccination serological screening for dengue immunity, unlike Dengvaxia™. However, access to Qdenga™ remains limited due to its high cost and the fact that it is not yet reimbursable for the general population. The vaccine is designed for subcutaneous administration and is given as a two-dose series, with the second dose administered three months after the first.

In theory, intradermal administration may elicit comparable immune responses while using a lower vaccine dose, owing to the high density of antigen-presenting cells in the dermal layer. Based on this rationale, investigators from multiple departments within the Faculty of Medicine have initiated a collaborative study to evaluate the immunogenicity and safety of intradermal Qdenga™ administration in healthy volunteers. Immune responses will be assessed at baseline, 30 days after the first dose, and 30 days after the second dose. All participants will receive the first dose subcutaneously as per standard practice, then be randomized to receive the second dose either subcutaneously or intradermally.

This study aims to enhance understanding of the immune response elicited by Qdenga™ given via different administration routes and to generate data that may inform future vaccine implementation strategies and potential dose-sparing approaches.

CONSORT FLOW Diagram

## 5.7 Research methodology

### 5.7.1 Study Design

Prospective observational study

### 5.7.2 Study Setting

Clinical research center, Prince of Songkla university

### 5.7.3 Study samples

#### 5.7.3.1 Inclusion Criteria

1. Thai adult aged 18-60 years with positive dengue IgG from screening test, who not previously received dengue vaccine.
2. The subjects are able to and willing to comply with the requirements of the clinical trial program and could complete the 3-month follow-up of the study.
3. Individuals who are in good health condition at the time of entry into the trial as determined by medical history, physical examination and clinical judgment of the investigator and meet the requirements of immunization
4. The subject can provide with informed consent and sign informed consent form

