#### 5.7.11 Ethical Consideration

- **Informed consent process**

1. The research team will announce and publicize the study through the Line account (@psucrc) and the Clinical Research Center website to invite individuals who may be interested in participating. Participants may contact the investigators or study nurses at any time if they have questions or concerns.
2. Individuals who wish to participate may register their interest through the Line account (@psucrc) or by emailing [contact]
3. The study nurse will provide the participant information sheet and invitation documents through a method convenient for the potential participant (e.g., email or Line). Those who agree to participate will sign the consent invitation document and return it to the Clinical Research Center.
4. The study nurse will schedule study visits according to the protocol. Appointments will be arranged on weekends or public holidays to facilitate participation and avoid the need for participants to take leave from work.
  - Transient vaccine viremia may occur following Qdenga vaccination. This condition has been reported in approximately 16% of individuals with prior dengue infection and 49% of those without previous dengue exposure. Symptoms typically begin during the second week after vaccination and last an average of four days. Reported symptoms

include headache, joint pain, myalgia, and rash. This event is less commonly observed after the second vaccine dose

- This study does not introduce additional risks beyond those associated with the standard use of the Qdenga vaccine, which is already approved for use in Thailand. Participants will be monitored and managed according to standard clinical practice. In the event of allergic reactions or other discomfort, investigators will provide appropriate medical care.
- Blood collection may cause mild discomfort at the puncture site, minor bleeding, or bruising lasting 3–4 days. Infection at the puncture site is rare. Some individuals may experience dizziness or fainting, particularly those with needle or blood phobia. These risks will be minimized by having experienced nursing staff perform all blood draws.

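### No planned analysis isolates the response to the second dose: Day 120 levels in IgG-positive, already primed adults are compared only between arms, with no pre-dose-2 value

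*Combined protocol and SAP*

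**What the plan says.** - **Population.** Section 5.7.3.1 admits "Thai adult aged 18-60 years with positive dengue IgG from screening test", with no earlier dengue vaccination.
- **Contrast.** Section 5.6: "All participants will receive the first dose subcutaneously as per standard practice, then be randomized to receive the second dose either subcutaneously or intradermally". The two arms in 5.7.10 are SC-ID and SC-SC; no arm omits dose 2.
- **Aim.** Both primary objectives in 5.4 (antibody and T cell) ask about the response following an intradermal second dose. Section 5.5 states that "the study hypothesizes that intradermal administration of fractional doses of the Qdenga vaccine after an initial SC dose will be immunogenic". Section 5.3 puts it comparatively: "a lower dose via this route could achieve adequate immunogenicity compared to the standard subcutaneous administration".
- **Outcome times.** Section 5.7.8 lists ELISA and ELISpot at days 0, 30 and 120. Section 5.6 agrees: baseline, 30 days after dose 1 and 30 days after dose 2.
- **Blood draws.** The blood collection text in 5.7.9 has a sample before the booster and another 30 days after vaccination. The visit table in 5.7.10, as it reads in the extracted text, marks blood at Day 0, at the dose 2 visit (Day 90) and at Day 120, with none at Day 30.
- **Analysis.** For quantitative variables 5.7.12 names Student's t-test or the Wilcoxon rank-sum test, with P<0.05 as significant. It gives no paired analysis, change across dose 2, baseline adjustment, margin or responder definition.
- **Size.** Section 5.7.6: 24 participants, 12 per group, on a pilot-study recommendation.

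**The concern.** The objectives ask what the second dose does; the analysis compares where the two arms end up. In people with natural immunity and a full subcutaneous first dose, those are different questions. If the subcutaneous second dose adds little to the readout, the arms will have similar Day 120 levels whether or not the intradermal dose worked. If it adds a moderate amount, 12 per arm may be too few to show the gap. In both cases a non-significant comparison could be taken as support for dose-sparing when it shows nothing of the kind.

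The Day 30 value does not fill the hole. A change from Day 30 to Day 120 combines any waning after dose 1 with any effect of dose 2, so a flat or falling profile would not mean that dose 2 was inert.

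**Working it through.** **1. The plan's own figure.** 12 × 2 = 24, as stated. No SD, effect, power or margin is given, so there is no power calculation to reproduce.

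**2. What each comparison contains.**

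| Comparison | Contains | Planned? |
|---|---|---|
| Day 120 level, SC-ID v SC-SC | prior infection + dose 1 + dose 2; route effect only through the between-arm gap | Yes (5.7.8, 5.7.12) |
| Day 30 to Day 120, within person | waning after dose 1 + dose 2 | Samples listed in 5.7.8; no paired analysis |
| Pre-dose-2 to Day 120, within person | 30-day change across dose 2 | Draw in 5.7.9 and 5.7.10; not an outcome, no analysis |

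**3. What the between-arm test can show if the intradermal dose is inert.** Let the subcutaneous second dose add *d* between-person SD at Day 120 and the intradermal dose add nothing. The t-test has 22 degrees of freedom and noncentrality *d*·√(12/2). Alpha is 0.05, taken as two-sided (sidedness is not stated).

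| *d* (SD) | Power | Non-significant although inert |
|---|---|---|
| 0.2 | 8% | 92% |
| 0.5 | 22% | 78% |
| 0.8 | 47% | 53% |
| 1.0 | 65% | 35% |
| 1.2 | 80% | 20% |

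The 95% CI half-width for the between-arm difference is 2.074 × √(2/12) = 0.85 SD. On a log10 scale with an assumed SD of 0.4 (range 0.3 to 0.5), a boost of 0.2 log10 gives power of 22% (16% to 35%). The 1.2 SD needed for 80% power is then 0.48 log10 (0.36 to 0.60), about 3-fold (2.3-fold to 4.0-fold). The documents give neither the boost nor the SD.

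**4. What the within-person change would offer.** With within-person correlation ρ, the SD of the change is √(2(1−ρ)) between-person SD. For one arm of 12 (11 degrees of freedom), the 95% CI half-width is 2.201 × √(2(1−ρ))/√12. For the between-arm difference in change it is 0.847 × √(2(1−ρ)). The values of ρ are assumptions.

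| | ρ = 0.5 | ρ = 0.7 | ρ = 0.9 |
|---|---|---|---|
| One-arm change: half-width (SD) | 0.64 | 0.49 | 0.28 |
| One-arm change: rise with 80% power (SD) | 0.89 | 0.69 | 0.40 |
| One-arm change: power for 0.5 SD | 35% | 53% | 94% |
| Difference in change: half-width (SD) | 0.85 | 0.66 | 0.38 |
| Difference in change: power for 0.5 SD | 22% | 33% | 75% |

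At ρ = 0.5 the difference in change is no more precise than the Day 120 comparison; it gains only above that.

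**5. Is a rise in the SC-SC arm enough to make similarity meaningful?** Simulation with an inert intradermal dose and a subcutaneous boost of 0.5 SD (0.2 log10 at SD 0.4): the SC-SC rise has a 95% CI above zero in 35%, 53% and 94% of trials at ρ = 0.5, 0.7 and 0.9. Among those trials the Day 120 comparison is still non-significant in 68%, 73% and 78%, against 78% in all trials. A rise in the control arm is necessary but says little about the intradermal dose.

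**The case against.** **The material for a check is there.** Sections 5.7.9 and 5.7.10 put a draw before dose 2, so a reader who infers that the study cannot detect a second-dose response goes too far. This stands. What is missing is the pre-dose-2 value as an outcome and an analysis that uses it.

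**The power figures are ordinary small-sample power.** They rest on assumed boosts, would be the same in seronegative people, and the protocol calls itself a pilot for preliminary estimates. This also stands; they show only how little a non-significant result would mean.

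**The plan never says that non-significance means adequacy.** True: 5.7.12 is a generic list of tests. But it offers no other route from data to the comparative hypothesis in 5.3, so the misreading is foreseeable.

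**Inferring that a further dose does little here.** The protocol reports that "49% of previously uninfected participants and 16% of those previously infected with dengue experienced vaccine viremia", says of viraemia that "This event is less commonly observed after the second vaccine dose", and gives month-36 DENV-4 seropositivity of "89.5% in seropositive individuals compared to 21.6% in seronegative individuals". A reader might conclude that the Day 120 level is mostly carry-over. The documents do not support that: viraemia is not an antibody or T-cell response, and the month-36 figures do not separate dose 2 from what came before. No data before and after dose 2 in seropositive adults are given.

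**The population is a defensible choice.** Section 5.5 gives a safety reason for a subcutaneous first dose and mentions possible use as a booster, which suits primed adults. The remark in 5.6 that no serological screening is needed describes the product, not the target population. Only the scope of the conclusions is at issue.

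**Conclusion.** The point holds as a gap in the analysis, not as a fatal flaw in the design. Nothing planned shows whether dose 2 raised either readout in either arm, although that is what both primary objectives ask. With 12 per arm, a non-significant Day 120 comparison would not show that the intradermal dose worked: an inert dose would escape detection more than half the time if the subcutaneous boost were 0.8 SD or less. The problem is conditional, since a boost of about 1.2 SD or more would usually expose an inert dose. These figures assume a two-sided 5% t-test, roughly normal outcomes (after log transformation if needed) and no dropout. The repair is cheap and worth making before analysis.

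**What to change.** 1. **Reconcile the sampling days.** Sections 5.6 and 5.7.8 list Day 30; 5.7.9 and the visit table in 5.7.10 point to a draw before dose 2. State which samples are taken, and add the pre-dose-2 sample to 5.7.8 as an outcome time point for ELISA and ELISpot.
2. **Add to 5.7.12, for each readout,** the within-person change from pre-dose-2 to Day 120 in each arm with a 95% CI. The SC-ID change is the direct answer to each primary objective; the SC-SC change shows whether the readout can register a second dose.
3. **Report the route comparison** as the between-arm difference in change, or as a Day 120 comparison adjusted for the pre-dose-2 value, with a 95% CI. The adjusted form is safer if the within-person correlation is low.
4. **State that non-significance will not be read as adequacy,** and do not treat an SC-SC rise above zero as enough to make similarity count as adequate.
5. **Limit conclusions** to dengue-seropositive adults primed with one subcutaneous dose.

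Cost: protocol wording, two estimates per readout and, if not already intended, ELISA and ELISpot on one more sample per participant. No extra participants or visits are needed. The downside is that the study may have to report an inconclusive comparison and make a narrower claim.
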